## **4 STUDY METHODOLOGY**

### **4.1 Study Design**

This is a prospective, multi-center study to evaluate the everlinQ endoAVF System when used to create an endoAVF for patients who require vascular access for hemodialysis. This study is a post-market study, and will be available to sites in selected regions where the product is available for use and properly registered or licensed (i.e. CE Mark, Health Canada License).

The study may have up to 20 active sites participating in order to enroll up to 200 patients that undergo endoAVF creation with the everlinQ endoAVF System. All patients who meet study inclusion criteria and no exclusion criteria will be considered a study candidate. Study candidates who undergo the everlinQ procedure (catheter insertion and delivery of RF energy) will be enrolled in the study. Study candidates who do not undergo the everlinQ procedure will be treated per physician and hospital guidelines and will not be considered enrolled in the study. All enrolled patients are expected be followed up to 12 months. Refer to Figure 1 for a flowchart overview of the study, and Table 2 for Withdrawal and Follow-Up Requirements.

**Figure 1: Study  
Flowchart**

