## **4.3 Study Outcome Measures**

All patients enrolled in the study and do not have a renal transplant, will be included in these outcome measurements unless otherwise noted.

**Primary Patency:** The interval from the time of access placement until any intervention designed to maintain or re-establish patency, access thrombosis, access abandonment, or the time of measurement of patency.

❖ **endoAVF abandonment definition:**

The endoAVF is considered abandoned if any of the following occur:

- The endoAVF is occluded and patency cannot be restored by any intervention, including medical, surgical, radiological or rest through the last follow up;
- The endoAVF is deemed inadequate for dialysis (for example, it never matures or is too deep for needle access) and the associated problem cannot be corrected by any intervention, including medical, surgical, radiological or rest;
- The endoAVF is ligated.

An endoAVF is not considered abandoned when it is not cannulated in subjects with a successful renal transplantation or when reasons of subject preference alone preclude cannulation.

**Assisted Primary Patency:** The interval from access placement to thrombosis or abandonment; not triggered by access circuit interventions performed in the absence of occlusion.

**Secondary Patency:** The interval from the time of access placement until access abandonment, loss to thrombosis, or the time of patency measurement including intervening manipulations (surgical or endovascular interventions) designed to re-establish functionality in thrombosed access.

**Functional Patency:** The interval of time from the first 2-needle dialysis utilizing the access until access abandonment.

**Procedure Success:** The successful creation of an endoAVF with blood flow confirmed intraoperatively by fistulography or by duplex ultrasound postoperatively.

**Time to Endovascular Fistula (endoAVF) Maturation (Vascular Access Usability):** Total time (number of days) from successful endoAVF creation to one of the following:

- Successful hemodialysis using 2 needle cannulation ***OR***
- Vascular accesses that is free of stenosis or thrombosis, with brachial artery flow of at least 500 ml/min and at least a 4.0 mm vein diameter as measured via duplex ultrasound.

**Time to Cannulation:** The time (number of days) from the index procedure (successful endoAVF creation) to the first use of the endoAVF for cannulation will be reported.

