**Number of Patients Who Met Functional Cannulation:** Functional Cannulation is defined as 2-needle access of the endoAVF access circuit with performance of  $\geq 2/3$ rds of  $\geq 120$  minute dialysis sessions through the endoAVF access circuit over a continuous 28-day period.

**Central Venous Catheter (CVC) Exposure:** CVC exposure will be analyzed at the follow-up time points, presenting the number/percent of patients reporting CVC use and the number/percent reporting dialysis access through other means, as well as the number/percent of subjects not yet on dialysis.

**Adverse Events:** Rate of serious procedure or device related Adverse Events (AEs) throughout the study period. The relevant events and rates of occurrence will be analyzed with a time component, to analyze procedural AEs and post-procedural AEs.

**Intervention Rate:** The percentage of patients requiring intervention will be calculated at 3, 6 and 12 months follow-up visits post index procedure. The rate of interventions that occurred during the index procedure and during short term follow-up will also be calculated.

The endoAVF-related interventions include:

- Interventions to maintain or restore patency of the endoAVF, including endovascular and surgical procedures designed to address occlusive thrombosis (resulting in absence of thrill or bruit at endoAVF) and clinically significant occlusive stenosis at or near endoAVF site.
- Interventions to support maturation of the arterialized vein segments, including endovascular procedures such as secondary coil embolization to facilitate flow into the target cannulation veins.
- Interventions to support cannulation of the arterialized vein segments, including procedures such as a superficialization or elevation where the target cannulation vein is brought closer to the skin surface to enable cannulation, without the creation of a new AV fistula.
- Any intervention to address any complications or adverse events of the access circuit.

**Note:** Any additional procedure performed at the time of the index procedure to address an adverse event will require a Post-Procedure Intervention eCRF to be completed.

**Note:** Diagnostic fistulogram, angiogram or duplex ultrasound will not be considered an intervention for the purpose of this study.

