## **5.4 Follow-Up Visits**

All enrolled patients that undergo a successful endoAVF creation will return for follow-up at 0-10 days post index procedure, then again at 21-45 days, 3, 6, and 12 months post index procedure. Refer to Table 1 for required testing at each follow-up visit.

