**Table 5-2: Withdrawal and Follow-Up Requirements**

If	Action Item
ICF was signed and the study catheter was not inserted.	The patient is not considered enrolled. Complete the Subject Screening Log as a screen failure.
The study catheter was inserted but RF energy was not delivered and therefore, the patient did not undergo endoAVF procedure (e.g., index procedure was aborted or converted to other surgical methods for AVF creation).	The patient is not considered enrolled. Complete the Subject Screening Log as a screen failure.
The study catheter was inserted and RF energy was delivered but the endoAVF was not created, with or without a reportable adverse event(s).	Patient is considered enrolled. Follow patient until protocol reportable AE resolves.  Collect all baseline-procedure and adverse event data and exit the patient (end date = date of AE resolution).
The study catheter was inserted and RF energy was delivered and endoAVF was successfully created.	Patient is considered enrolled. Follow all required visits per Study Protocol.
endoAVF was successfully created (patient enrolled) and there is a permanent loss or abandonment of the endoAVF	Patient participation ends. Complete Follow up forms as appropriate until loss of endoAVF, then complete an End of Study eCRF.

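### Enrolled patients with RF delivered but no fistula have no defined safety follow-up, so delayed serious related events can go uncollected while these patients remain in the adverse event rate

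*Combined protocol and SAP*

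**What the plan says.** Section 4.1 defines enrolment by the procedure, not by its result: "Study candidates who undergo the everlinQ procedure (catheter insertion and delivery of RF energy) will be enrolled in the study". It adds "All enrolled patients are expected be followed up to 12 months", and the next sentence sends the reader to the withdrawal and follow-up table (cited there as Table 2, numbered 5-2 in the text).

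Table 5-2 has a row for patients in whom "RF energy was delivered but the endoAVF was not created, with or without a reportable adverse event(s". The action is "Patient is considered enrolled. Follow patient until protocol reportable AE resolves". The site then collects the baseline, procedure and adverse event data and is to "exit the patient (end date = date of AE resolution".

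Section 5.4 limits the visit schedule: "All enrolled patients that undergo a successful endoAVF creation will return for follow-up at 0-10 days post index procedure", with the later visits following for the same group.

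Section 4.3 sets the population for all outcome measures: "All patients enrolled in the study and do not have a renal transplant, will be included in these outcome measurements unless otherwise noted". The adverse event measure is "Rate of serious procedure or device related Adverse Events (AEs) throughout the study period", to be split into procedural and post-procedural events, and it notes no exception for failed creations. Section 6 counts an adverse event only if it arises during the study. Section 7 has no time-at-risk or censoring rule written for adverse events.

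**The concern.** The Table 5-2 row covers patients with an adverse event and patients without one, but its only end date is the resolution of an event. For a patient without an event that date does not exist, and Section 5.4 supplies no visit that would keep the patient in the study. A patient who did have an event leaves when it resolves, so a second, later event would also fall outside collection.

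These patients have had the same catheter insertion and RF delivery as everyone else. Section 3.2 lists complications such as pseudoaneurysm, infection, and vessel or nerve damage, which may declare themselves after discharge. Section 6 itself judges one symptom group over weeks: transient numbness, tingling or coolness is exempt only if it has gone within 4 weeks, and that cannot be established in someone who has already left.

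At stake is the post-procedural part of a listed safety outcome. The study tests no hypotheses, and Section 4.2 says its data may support reimbursement and publications, so the accuracy of the reported rates is its main product.

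**Working it through.** **Reading the passages together**

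1. RF delivered, no fistula: enrolled (Section 4.1, Table 5-2).
2. Scheduled visits: none, not even at 0-10 days (Section 5.4).
3. End of observation: resolution of the adverse event if there is one, otherwise undefined (Table 5-2).
4. Events after exit: not collected (Section 6). Section 5.5 asks for reporting at unscheduled visits, but only within the follow-up period.
5. Denominator: all enrolled patients without a renal transplant, with no exception noted for adverse events (Section 4.3).

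The numerator can therefore lose events from patients who stay in the denominator.

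**Size**

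The plan gives no failure rate, adverse event rate or sample-size calculation, so there is no figure to reproduce. From the documents: N = 200 (maximum enrolment). Assumed: f, the share of enrolled patients with failed creation who are unobserved after exit; q, the late-event risk in patients with a fistula; RR, the relative risk in failed creations.

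- Crude observed rate = (1 - f) × q
- Full-cohort rate = (1 - f) × q + f × q × RR
- Shortfall = f × q × RR, which is downward for any RR above zero

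Patients affected, as an upper bound because those with an open event are followed until it resolves:

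- f = 2%: 200 × 0.02 = 4
- f = 10%: 200 × 0.10 = 20

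Crude rate with q = 5% and RR = 1:

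- f = 2%: 0.98 × 0.05 = 4.9%
- f = 10%: 0.90 × 0.05 = 4.5%

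Middle case, f = 5% (10 patients), q = 5%:

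| | RR = 1 | RR = 2 |
|---|---|---|
| Crude observed rate | 4.75% | 4.75% |
| Full-cohort rate | 5.00% | 5.25% |
| Expected missed events | 10 × 0.05 = 0.5 | 10 × 0.10 = 1.0 |
| Chance of missing at least one | 1 - 0.95^10 = 40% | 1 - 0.90^10 = 65% |

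Over f = 1-10%, q = 2-10% and RR = 1-2, the shortfall runs from 0.01 × 0.02 × 1 = 0.02 to 0.10 × 0.10 × 2 = 2.0 percentage points, or 1% to 18% of the full-cohort rate.

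**What an at-risk denominator would do**

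Dropping exited patients from the denominator gives (1 - f)Nq / ((1 - f)N) = q. In the middle case that is 5.00%. The dilution is gone if RR = 1, but 0.25 points of shortfall remain if RR = 2. The missed events stay missed in both cases.

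**The case against.** Several points on the other side are sound.

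- **Exit on day 0 is not stated.** A reader might infer that patients without an adverse event leave at once by rule. Table 5-2 is silent. Early exit is the natural reading, since no visit is required and nothing is being followed, but what the text supports is an undefined end date.
- **Not all failed creations go unobserved.** A reader might take 4-20 as the number with no observation after the procedure. Those with a reportable event are followed until it resolves, so this is a ceiling, and it rests on assumed failure rates.
- **Higher risk is not documented.** It is tempting to call failed creations a higher-risk group. Nothing in the documents says so, and several Section 3.2 risks, such as steal, venous hypertension and heart failure from fistula flow, largely presuppose a working fistula. The risk could be lower. The point does not need excess risk.
- **Section 4.1 is not a flat contradiction.** Its 12 months is a ceiling, and the next sentence defers to the table. Table 5-2 and Section 5.4 agree with each other. The general sentence needs aligning, no more.
- **The denominator is not settled.** Section 4.3 gives adverse events a time component, and Section 7 uses Kaplan-Meier for time variables. Censoring at exit would reduce the dilution. Section 7 does not say adverse events are handled this way, and censoring recovers no uncollected event.
- **The shift is small.** At q = 5%, with 10 events in 200, the exact 95% interval is roughly 2.4% to 9.0%. A shift of 0.1-0.5 points lies well inside it.

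Ending fistula follow-up when there is no fistula is also a defensible choice in an observational study. It does not explain why safety observation has no defined end.

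**Conclusion.** The gap holds. Enrolled patients with RF delivered and no fistula have no scheduled safety contact and, without an adverse event, no end date, yet by the general rule of Section 4.3 they count in the serious related adverse event rate. Any error in a crude post-procedural rate is one-directional: it can only be too low.

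The effect on the overall rate is probably small: 0.1-0.5 percentage points for an assumed 5% late rate, equal risk and 2-10% failure, with at most 4-20 of 200 patients concerned. All of these rates are assumptions, and the dilution also assumes a crude all-enrolled denominator. The practical loss is more likely to be one or two unseen serious events than a materially wrong percentage. The correction is cheap and should be made, but the gap does not undermine the study's other outcomes.

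**What to change.** Amend Table 5-2 and Section 5.4, and align the general follow-up sentence in Section 4.1, so that:

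- enrolled patients without a fistula have adverse event status checked by phone or from records over the existing Visit 1 (0-10 days) and Visit 2 (21-45 days) windows, without duplex ultrasound;
- every such patient has an explicit end date, whether or not an adverse event occurred, and an event still open at the second contact is followed to resolution as now.

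In Sections 4.3 and 7, state that post-procedural adverse event rates use patients under observation, or patient-time, as the denominator. This is still needed after the added contacts, because these patients would leave by about day 45 while others continue to 12 months.

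The cost is a wording change and one or two contacts for a small number of patients, with no new procedure. Events after the second contact would still not be collected.

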**Table 5-1: Schedule of Study Procedures**

Assessment	Screening	Index Procedure	Post Index Procedure				
			0-10 Days Visit 1	1 Month Visit 2	3 Month Visit 3	6 Month Visit 4	12 Month Visit 5
Compliance Window	-60 days	day 0	0-10 days	21-45 days		Anniversary date +14 days	
Informed Consent	X						
History, Physical Exam, Pregnancy Test	X						
Blood Pressure	X	X	X	X	X	X	X
HTN Medications	X	X	X	X	X	X	X
DUS Evaluation	X	X 	X	X	X	X	X
Angio/Venography		X					
Adverse Events		X	X	X	X	X	X
Allen's Test /Palmar Arch	X	X	X	X	X	X	X
Dialysis Access Data				X 	X 	X 	X 
QOL Questionnaire	X				X	X	X

 Recommended post-procedure to confirm absence of bleeding or hematoma formation

 All efforts by the site must be undertaken to provide this data to the sponsor, minimally over a continuous 28-day period.

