### **5.8 End of Study**

The End of Study eCRF is required to be completed whenever a patient exits the study. This includes patients enrolled in the study who:

- Complete the study protocol, after 12 months of follow up
- Voluntarily withdraw from the study
- Withdrawn by the study Investigator
- Met the definition of endoAVF abandonment (see Section 4.3)
- Lost to follow-up
- Deceased
- Other reason(s) for exiting the study

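### CVC status is not collected after patients exit because the endoAVF was lost or never created, although Section 4.3 includes all enrolled non-transplant patients and sets no CVC denominator

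*Combined protocol and SAP*

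**What the plan says.** **Population.** Section 4.3 opens its outcome list with a general rule: "All patients enrolled in the study and do not have a renal transplant, will be included in these outcome measurements unless otherwise noted". The CVC paragraph notes no exception and names no denominator. It says "CVC exposure will be analyzed at the follow-up time points, presenting the number/percent of patients reporting CVC use", together with the numbers and percentages using other access and not yet on dialysis.

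**Exit.** Table 5-2 counts a patient as enrolled once the catheter is in and RF energy has been delivered. Two routes then lead out of the study because of the access itself.
- If the endoAVF was not created, the site is told: "Collect all baseline-procedure and adverse event data and exit the patient (end date = date of AE resolution".
- If it was created and then permanently lost or abandoned: "Patient participation ends. Complete Follow up forms as appropriate until loss of endoAVF, then complete an End of Study eCRF".

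Section 5.8 confirms abandonment as an end-of-study reason.

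**Data collection.** Section 5.4 limits visits to patients with a created fistula: "All enrolled patients that undergo a successful endoAVF creation will return for follow-up". Table 5-1 schedules Dialysis Access Data at 1, 3, 6 and 12 months, with the footnote "All efforts by the site must be undertaken to provide this data to the sponsor, minimally over a continuous 28-day period". It makes no provision for patients who have left. Sections 5.6 and 5.7 say that data obtained before exit or withdrawal are used. Section 7 summarises categorical variables by frequencies and percentages and has no rule for access status after exit.

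**Duration.** The Protocol Summary lists the outcome as duration of CVC exposure. Section 4.3 defines only percentages by time point.

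**The concern.** Exit is triggered by failure of the access, and CVC use is one of the things that may follow such failure. The Introduction itself says that when an AVF fails to mature in a patient who needs hemodialysis at once, a tunneled catheter must often be placed. The missing patients are therefore not a random subset with respect to this outcome.

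Exits accumulate, so each later time point lacks CVC status for more of the enrolled cohort. Depending on the denominator, the reported percentage can move between visits when nobody's access has changed. Section 4.2 says the data may support reimbursement and publications. A reader who relies on the opening rule of Section 4.3 could take a 12-month CVC percentage to describe all enrolled non-transplant patients, which the collected data cannot do.

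**Working it through.** **1. Is there a plan figure to reproduce?** No. The study tests no hypotheses, 200 is an enrolment ceiling, and the documents give no exit rate and no CVC rate. Every rate below is an assumption.

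**2. Set-up.** At a given time point let L be the share of enrolled patients already exited because the endoAVF was lost or not created, r the CVC proportion among those retained, and c the CVC proportion among those exited. Deaths, transplants, withdrawals and missed visits are ignored for simplicity.

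All-patient proportion = (1 - L)r + Lc.

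**3. Two readings of the denominator.**
- *Attenders.* Reported figure = r. Bias = r - [(1 - L)r + Lc] = -L(c - r). This is negative if c > r, zero if c = r and positive if c < r.
- *All enrolled, no post-exit data.* Exited patients are in the denominator but cannot be counted as CVC users. Reported figure = (1 - L)r. Bias = -Lc, which is negative or zero.

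**4. Bounds with no assumption about c.** Letting c run from 0 to 1, the all-patient figure lies between (1 - L)r and (1 - L)r + L, a width of L.

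**5. Illustration.** N = 200, 20 exited (L = 10%), 27 CVC users among 180 retained (r = 27/180 = 15%). The attender reading reports 15.0%; the all-enrolled reading reports 27/200 = 13.5%.

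| Assumed c | All-patient figure | Bias, attenders (points) | Bias, all enrolled (points) |
|---|---|---|---|
| 0% | 27/200 = 13.5% | +1.5 | 0 |
| 15% | 30/200 = 15.0% | 0 | -1.5 |
| 50% | 37/200 = 18.5% | -3.5 | -5.0 |
| 100% | 47/200 = 23.5% | -8.5 | -10.0 |

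The bounds are 13.5% to 23.5%, a width of 10 points = L.

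**6. Wider assumptions, L = 20%.** On the attender reading, r = 5% with c = 100% gives -0.20 x 0.95 = -19 points, and r = 50% with c = 0 gives +0.20 x 0.50 = +10 points. On the all-enrolled reading the same two cases give -20 and 0 points.

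**7. Drift with no change in access.** Suppose 60 of 200 (30%) use a CVC throughout and 20 patients exit.
- If all 20 use a CVC, attenders give 40/180 = 22.2% and all enrolled give 40/200 = 20.0%.
- If none does, attenders give 60/180 = 33.3% and all enrolled give 60/200 = 30.0%.

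**8. Duration.** A patient who exits at month 3 leaves 12 - 3 = 9 months unobserved, and one who exits at month 9 leaves 3. Anywhere from none to all of that may be catheter time.

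**The case against.** **Ending follow-up when the studied access ends is a deliberate and ordinary choice in an observational study.** That is fair for patency: abandonment is itself a terminal event there, so exit at abandonment does no harm to the Kaplan-Meier estimates. (How not-created patients enter patency is a separate question.) CVC status at a visit is a different kind of outcome, and the defence does not carry over to it.

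**The plan says something about exits.** Sections 5.6 and 5.7 keep data from before exit or withdrawal, and Table 5-2 asks for follow-up forms until loss, so CVC use up to loss still counts. This stands, but it supplies nothing afterwards. Section 4.1 says follow-up is up to 12 months and points to the withdrawal table, so an attentive reader is warned that not everyone reaches month 12.

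**Not every failing fistula leaves.** A fistula judged inadequate counts as abandoned only if "the associated problem cannot be corrected by any intervention, including medical, surgical, radiological or rest" applies. The occlusion criterion requires that patency cannot be restored through the last follow-up, so some exits may come late. Patients with a problem still thought correctable, or awaiting a 2nd-stage procedure, stay in and may be recorded as using a CVC. This limits the loss without removing it.

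**Two stronger readings are tempting.** A reader might infer that the later percentages will cover only patients with a functioning or salvageable endoAVF. The text does not settle that: the default in Section 4.3 is all enrolled non-transplant patients, while wording about patients reporting at follow-up time points suggests attenders. A reader might also infer that CVC use will certainly be understated. The Introduction makes that plausible, but exited patients may have other access or not yet be on dialysis, and on the attender reading the bias reverses if c < r.

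**Conclusion.** The point holds in this form. The population in Section 4.3 and the exit rules in Table 5-2, Section 5.4 and Section 5.8 do not fit together for the CVC outcome. After exit, CVC status is missing for patients selected on access failure, and any CVC duration is cut off at exit.

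The bias is -L(c - r) on the attender reading and -Lc on the all-enrolled reading. Its size is unknown because the documents give no value for L, r or c, and its direction is settled only on the second reading, where it is an understatement or zero. What can be said without guessing c is that the all-patient percentage is uncertain by L points.

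No hypothesis test depends on this, and it does not undermine the study. In a purely descriptive study, though, an outcome percentage needs a stated denominator and an account of who is missing. It should be fixed.

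**What to change.** **In Section 4.3:**
- State the CVC denominator at each time point as all enrolled non-transplant patients alive and not withdrawn. Say that withdrawn means withdrawal by the patient or the investigator, not exit because the endoAVF was lost or not created. Since nothing is collected after exit, alive and non-transplant have to mean not known otherwise.
- Report categories that sum to that denominator: CVC; other access; not yet on dialysis; exited because the endoAVF was lost or not created (access unknown); lost to follow-up or missed visit (unknown).
- Give bounds over the unknown categories: known CVC users divided by the denominator, and known CVC users plus all unknowns divided by the denominator.
- Label any attender-only percentage as conditional on remaining in follow-up, and any CVC duration as observed only to exit.
- Reconcile the opening all-enrolled sentence with the exit rules.

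No new data are needed. Abandonment is already an End of Study reason. Not-created patients should be taken from the Table 5-2 exit category rather than from Procedure Success, which also requires confirmed flow.

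**Optional:** record access type and CVC status and dates from charts or by telephone at the remaining Table 5-1 time points, with no added procedures. This narrows the bounds, but it means amending Table 5-2 and Sections 5.4 and 5.8, and it depends on EC approval and on patients' consent to collection after exit.

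**Cost:** the first part is a small protocol edit, which Section 8.4 makes subject to sponsor and EC approval. The CVC figures will carry wider stated uncertainty and may look less favourable. The optional part adds modest site effort.

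### Table 5-2 ends participation when the endoAVF is lost or ligated, even with an adverse event still open, so the later course of that event need not be collected

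*Combined protocol and SAP*

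**What the plan says.** Table 5-2 gives different exit rules to two groups of enrolled patients.

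- RF energy delivered, no fistula created: "Follow patient until protocol reportable AE resolves". Baseline, procedure and AE data are collected, and the instruction is then to "exit the patient (end date = date of AE resolution").
- Fistula created and later lost for good or abandoned, where the stated action is: "Patient participation ends. Complete Follow up forms as appropriate until loss of endoAVF, then complete an End of Study eCRF". AE status is not mentioned.

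The abandonment definition in Section 4.3 has three limbs. One is simply "The endoAVF is ligated". Another is "The endoAVF is occluded and patency cannot be restored by any intervention, including medical, surgical, radiological or rest through the last follow up". The third is a fistula judged inadequate for dialysis that cannot be corrected. Section 5.8 lists "Met the definition of endoAVF abandonment (see Section 4.3") among the reasons for study exit, with no exception for an unresolved AE.

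The safety outcome in Section 4.3 is the "Rate of serious procedure or device related Adverse Events (AEs) throughout the study period". Section 4.1 expects every enrolled patient to be followed for up to 12 months.

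**The concern.** Section 3.2 names steal or ischemia, venous hypertension, infection, nerve damage and heart failure from access flow as risks. If a fistula is ligated because of such a complication, the ligation is itself the event that ends participation. The patient can then leave the study while the AE is still running.

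This matters because the outcome counts serious events. Under Table 6-1, seriousness can turn on permanent impairment, a hospital stay, or an intervention to prevent lasting harm. Some of these may be known only after the fistula has gone. A complication of the ligation would also fall after exit. Section 7 does not say how shortened AE observation is handled. In a simple percentage, patients who exited stay in the denominator and are treated as event-free from then on. In a time-to-event analysis they are censored at a time that can depend on the complication itself, so the censoring is informative.

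**Working it through.** The plan gives no figure for this point: no expected abandonment rate, no expected share of losses with an open AE, and no power calculation. The check is therefore a reading of the text, with one illustration of scale.

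**Step 1: the two rows compared.**

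| | RF delivered, no fistula | Fistula created, then lost |
|---|---|---|
| Enrolled | Yes | Yes |
| Open AE mentioned | Yes | No |
| Forms run until | AE resolution | Loss of the fistula |
| Exit date tied to | AE resolution | Loss or abandonment |

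**Step 2: does another section supply the missing rule?**

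- Section 5.5 covers unscheduled visits and outside medical records, but within the follow-up period.
- Section 5.7 uses the data available at withdrawal and asks for nothing later.
- Section 5.8 repeats abandonment as an exit reason, without an AE exception.
- Section 6 limits AEs to those arising in the course of the study and relevant to the procedure, device, access site or fistula. It has no rule to follow an AE to its outcome.
- Sections 6.1 and 8.3 have the Clinical Events Committee (CEC) adjudicate reported events, so it cannot judge a course that was not collected.
- Table 8-1 requires SAE and SADE reports within 10 working days of the investigator learning of the event. It sets no duty to follow the event afterwards.

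None requires an AE to be followed after exit for loss of the fistula.

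**Step 3: what is kept and what can be missed.** An AE that starts before or at the loss falls within active collection. It goes on an AE form and to the CEC. What can be missed is (a) its course and resolution, (b) a later change from non-serious to serious, and (c) new related events after exit, for example after ligation.

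**Step 4: how sharp the exit date is.** Ligation gives an exact date. The occlusion and inadequacy limbs require that no intervention can correct the problem, so the exit date is less sharp and some AE follow-up may continue while repair is attempted. The gap is clearest for ligation.

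**Step 5: scale.** The enrollment cap of 200 comes from Section 4.1; the loss rates are assumed.

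- Patients exiting under the last row, at an assumed 5% to 30% loss: 0.05 × 200 = 10 to 0.30 × 200 = 60.
- The share of these with an unresolved AE is unknown.
- Effect on the rate of one patient whose only serious event is missed: 1/200 = 0.5 percentage points. The effect is larger if fewer than 200 are enrolled or transplant recipients are left out under Section 4.3.

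**The case against.** The strongest reply is that little of consequence is lost. A complication bad enough to end the fistula happens while collection is running. It is recorded and adjudicated, and it may already be serious under Table 6-1 because it led to hospitalization or to an intervention to prevent lasting harm. In a rate of patients with a serious event, further worsening of the same event then adds no patient. This stands. A reader might infer that the complications that end fistulas go unrecorded, or that serious AEs are shown to be under-counted; the documents support neither. Under-counting is possible only through a later upgrade or a new event after exit.

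A second reply is that the rows differ for a reason. Section 5.4 gives scheduled visits only to patients with a successful creation, so the AE clause is the only follow-up for the other group. This explains how the rows may have come about and argues against an intended conflict. It does not explain why an open AE is dropped in one row and followed in the other.

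A third is that the row is merely silent on open AEs, that forms are to be completed as appropriate, and that the Table 8-1 reporting duty is not expressly confined to active participants. These soften the point. But the row ends participation without condition, and no text overrides it.

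Finally, loss of observation could be put in patient-years. Assuming 5% to 20% abandonment with 6 to 9 months remaining gives 10 × 0.5 = 5 to 40 × 0.75 = 30 of at most 200 patient-years, or 2.5% to 15%. That is calendar time, much of it without a working fistula, and should not be read as a share of events lost.

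**Conclusion.** The point holds as a narrow gap in safety data collection. Table 5-2 lets a patient exit at loss or ligation with an unresolved AE, while another row of the same table follows such an AE to resolution, and no other section reconciles the two. The serious AE rate can be biased downward and some AE outcomes can remain unknown. Neither the direction of any actual error in this study nor its size can be established from the documents: the loss rates used above are assumptions, and the share of losses with an open AE is not known. The study is descriptive and tests no hypothesis, so no inference is overturned. What is affected is the completeness of one stated outcome. It is worth correcting mainly because the correction is cheap.

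**What to change.** Reconcile the two rows of Table 5-2 and Section 5.8. In the last row, and in Section 5.8 for exits due to abandonment, separate the two kinds of follow-up. Suggested wording: *Patency follow-up ends at loss or abandonment. Any open protocol-reportable AE is followed until it resolves or stabilises; the End of Study eCRF is then completed.* The words on stabilising are needed because a permanent impairment never resolves and would otherwise leave follow-up without an end.

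In the report, give the number of patients who exit with an unresolved AE, and state how AE observation after loss of the fistula is treated in the rate.

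The cost is protocol and eCRF wording plus AE-only follow-up, confined to patients with an open AE at loss. No imaging or procedure is added. An AE-only contact at 12 months for every patient with an abandoned fistula would also pick up new events after exit, but it is optional: the table does not require it for the no-fistula group, whose follow-up stops at AE resolution.
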